First day of new management plan (Visit 6)

This will be performed as per standard of care and may be the same date as Visit 4, if the new management plan is commenced on the same day as the agreed treatment decision. During this visit, the investigator will record the date of management starting (to determine when follow-up information should be collected as detailed in the next heading “Clinical follow-up”).

Where patients are commencing radical salvage therapy, the investigator will also ensure that a pre-treatment PSA has been measured and recorded up to 31 days before this date.

All patients who receive radical salvage therapy

In this patient group, PSA will be measured a maximum of 31 days before therapy and at least once between 7-8 months after treatment completion. Where possible, this should be arranged to coincide with treatment-associated hospital visits as per standard of care. If these cannot be incorporated into the hospital visits, a minimum of one, maximum of two extra visits will be required for these PSA tests.

If the actual treatment received by the subject differs to the plan agreed at Visit 4, then this will be recorded on the “End of study” CRF (see the next section “Clinical follow-up”), along with the reason.

Clinical follow-up

Following instigation of their management plan, patients will be seen for follow-up at intervals as per standard of care and have imaging tests as clinically appropriate and per standard of care.

At the end of specified follow-up windows, follow-up information will be obtained by the local study team via attendance for imaging tests and via the GP or hospital medical care team as appropriate and entered on the “End of study” CRF. The patient will not be required to make a dedicated visit for this. The follow-up window is dependent on the type of management:

1. Radical salvage therapy: Up to the date of post-treatment PSA level check (7-8 months after completion of treatment).
2. Non-salvage management: Up to 6 months after Visit 6 (instigation of management plan).

In the event where radical salvage therapy is stopped prematurely or deemed by the clinical team to be sub-optimally delivered, the follow-up window should apply as for non-salvage management (up to 6 months from instigation of the initial management plan). The reasons for this should be recorded on the CRF as described in the prior section “All patients who receive radical salvage therapy”.

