The following information will be collected for all patients:

1. Copies of imaging tests and reports, and histopathological reports for relevant endpoint analyses
2. PSA levels
3. Mortality (if applicable)
 - a. Date of death
 - b. Causes of death
 - c. Other significant conditions contributing to death
 - d. Source of report
 - e. Whether the death was expected
 - f. Whether a causal relationship to the study IMP is suspected
 - g. Name of the investigator responsible for assessing expectedness and causality (if the patient died prior to the last research scan or as a result of an ongoing reportable AE)

In addition, the following information on effect of management will be collected:

Radical salvage therapy	Non-salvage management
Effect of radical salvage therapy: 
 a. Treatment response 
 I. $\geq 50\%$ decline in PSA [5] \pm II. Radiological response b. Treatment failure 
 I. Increase or $< 50\%$ decline in PSA \pm II. Radiological progression 	Effect of management as assessed by the clinical team: 
 a. Response 
 I. $\geq 50\%$ decline in PSA \pm II. Radiological response b. Stable c. Progressed 
 I. PSA progression and/or II. Radiological progression d. Not assessed

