7.10. Definition of End of Study

The fluciclovine (^{18}F) injection administration will be followed by a follow-up period which will continue for 6 months after instigation of management plan.

The end of the trial for an individual patient is defined as 6 months after instigation of their management plan. In patients who receive radical salvage therapy, the end of the trial is defined as the date of post-treatment PSA level.

The end of the study is defined as the date of database lock for data analysis, which is anticipated to occur within 12 weeks after the last patient has completed the 6 months post treatment follow up.

8. Risks and Benefits to Trial Participants

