11.2. Analysis of Outcome Measures/Endpoints

Evaluable patients are those that have had all baseline study measures recorded, including having had a fluciclovine (¹⁸F) PET/CT scan.

Evaluation of fluciclovine (¹⁸F) PET/CT

Evaluation of the fluciclovine (¹⁸F) PET/CT images will be primarily reviewed by site-based investigator(s) (as per standard of care). Image interpretation will be based on guidelines derived from an international fluciclovine (¹⁸F) reader consensus meeting held in June 2014. All readers will undergo training in interpretation of fluciclovine (¹⁸F) scans, and will have a training set available for reference. The investigators will have access to all the conventional imaging and medical record information.

The summary of findings will be documented on the appropriate CRF, in addition to a conventional imaging report issued as per standard of care in the respective institution.

Primary endpoint

The primary endpoint of clinical impact of fluciclovine (¹⁸F) in affecting treatment decisions will be assessed by record of the revised treatment plan post fluciclovine (¹⁸F) PET/CT scan in comparison to the pre-scan intended treatment plan.

Secondary endpoints

Improvement in outcome of radical salvage treatment based on fluciclovine (¹⁸F) PET/CT being included in the assessment.

This will be assessed as the proportion of these patients who have a treatment response or treatment failure, using the following definitions:

1. Treatment response
 - a. ≥50% decline in PSA [5] ±
 - b. Radiological response
2. Treatment failure
 - a. Increase or <50% decline in PSA ±
 - b. Radiological progression

PSA threshold

The positive detection rate will be calculated for the overall cohort and across a range of PSA values, to determine the optimum PSA threshold for lesion detection.

Safety assessment

Safety will be assessed from data on the occurrence of adverse events (AEs) and changes in clinical laboratory tests, vital signs, injection-site status, and physical examination findings from the time of administration of fluciclovine (¹⁸F) injection throughout the study period. This has been described in detail in Section 9.

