5.4.2 Secondary Efficacy Analyses

5.4.2.1 Treatment response as assessed by change in PSA

An assessment of treatment response, which is based on the percentage change in PSA from baseline to the last value reported, is defined as:

- >=30% decrease in PSA will be considered to be a response to treatment
- <25% increase or <30% decrease will be classified as stable disease
- >=25% increase in PSA will be classified as disease progression

See section 2 General Principles for baseline definition.

The number, percentage and exact 95% CI of subjects having a treatment response, stable disease and disease progression, as assessed by change in PSA, will be presented overall and separately for subjects in the FAS who had salvage treatment, for subjects who had non-salvage treatment, for those with a change in management plan and for subjects with no change in management plan following the ¹⁸F-fluciclovine PET/CT scan. In addition, treatment response assessed by change in PSA will be summarised by disease location (local disease versus extra-prostatic disease) and treatment administered.

The percentage change in PSA from baseline to the last value reported will be summarised overall and by subjects who had a change in management plan versus those who did not have a change in management plan following the ¹⁸F-fluciclovine PET/CT scan, disease location and treatment administered.

Finally, a waterfall plot of the maximum percentage reduction in PSA during the 4-8 month window will be presented on the y-axis and each subject will be represented by a bar on the x-axis. The bars will be ordered in descending order of the magnitude of the percentage change in PSA value.

Treatment response and the factors used to assess the response will be listed in full.

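### Salvage patients whose treatment is stopped early or judged sub-optimal move to a follow-up window that closes before the endpoint PSA, and their place in the salvage response analysis is undefined

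*Protocol*

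**What the plan says.** Protocol 7.7 (Clinical follow-up) sets two windows by type of management. For radical salvage therapy it is "Up to the date of post-treatment PSA level check (7-8 months after completion of treatment"). The other is "Non-salvage management: Up to 6 months after Visit 6 (instigation of management plan"). A further rule covers salvage therapy that is stopped prematurely or is "deemed by the clinical team to be sub-optimally delivered, the follow-up window should apply as for non-salvage management", counted from the start of the initial plan. The reasons go on the CRF.

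Elsewhere the 7-8 month PSA carries no exception. Protocol 7.7, under the sub-heading *All patients who receive radical salvage therapy*, requires PSA "at least once between 7-8 months after treatment completion"; Protocol 5.1 says the same. Protocol 7.10 adds: "In patients who receive radical salvage therapy, the end of the trial is defined as the date of post-treatment PSA level".

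The secondary endpoint is the proportion with a sustained response to radical salvage therapy. Of its analysis, Protocol 11.2 says: "This will be assessed as the proportion of these patients who have a treatment response or treatment failure". The outcome table in 7.7 has a two-class salvage column (response or failure). The non-salvage column, headed "Effect of management as assessed by the clinical team", has response, stable, progressed and not assessed.

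SAP 5.4.2.1 replaces both with one PSA scale: a decrease of 30% or more is response, an increase of 25% or more is progression, and anything between is stable. It is applied to the last PSA reported. Results are shown overall and "separately for subjects in the FAS who had salvage treatment, for subjects who had non-salvage treatment". SAP 5.4.3 rules out imputation. SAP Addendum 2 (Change 1) adds another table restricted to subjects who had salvage therapy.

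**The concern.** Whether a salvage patient is followed to the endpoint PSA depends on something that happens after treatment starts. One trigger, early stopping, is at least an observable event. The other is an opinion of the treating team in an open-label study. It has no stated criterion, and nothing requires it to be recorded before a post-treatment PSA is seen.

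Patients who stop early or are poorly treated may well be more likely to fail. If their outcome is measured earlier than everyone else's, or is missing, the salvage response rate mixes time points or drifts towards a rate among completers. A sustained response cannot be shown for patients whose data collection ends before the PSA meant to show it. Because the protocol passages disagree, sites may also handle the same patient differently.

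**Working it through.** **Plan's own figure.** The documents give no sample size or expected rate for the salvage response endpoint. The one stated size, for the primary endpoint, reproduces: 1.96² × 0.20 × 0.80 / 0.06² = 170.7, rounded up to 171, and 171 / 0.95 = 180. It has no bearing here.

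**Step 1: does the switched window exclude the endpoint PSA?** Inputs are from Protocol 7.7. Let treatment start at month 0 and last *c* months (*c* ≥ 0).
- Switched window closes at month 6 at the latest.
- Endpoint PSA is due from month *c* + 7 to month *c* + 8.
- Gap = (*c* + 7) − 6 = *c* + 1 months to the earliest due date, and *c* + 2 to the latest.

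Even with *c* = 0 the window closes 1 month before the PSA is first due, and a longer course widens the gap. No switched patient can have the scheduled PSA inside the window.

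**Step 2: are the passages compatible?**
- 7.7, Clinical follow-up: exception for stopped or sub-optimal therapy, 6 months from plan start.
- 7.7, All patients who receive radical salvage therapy: PSA at 7-8 months, no exception.
- 5.1: same PSA, no exception.
- 7.10: trial ends for salvage recipients at the post-treatment PSA, no exception.

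Within 7.7 one can read a general rule followed by an exception. Sections 5.1 and 7.10 cannot be read that way.

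**Step 3: what does the SAP do with these patients?**
- Scale: one for all subjects, so which protocol column applies has no effect on the SAP table.
- Time point: last PSA reported. If data stop at the switched window, that value comes from within 6 months of the start, beside values taken 7-8 months after completion.
- Missing PSA: no imputation, so no response class.
- Group: the salvage group is not defined, in 5.4.2.1 or in Addendum 2. The default denominator in SAP 2, the whole analysis set, does not settle it.

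**Step 4: how large could a denominator effect be?** The number of salvage starters, the true response rate *R*, the share *f* switched and the share *q* of those who are failures are all assumptions. If the switched patients are dropped:

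rate = (*R* − *f*(1 − *q*)) / (1 − *f*)

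| Case | *f* = 5% | *f* = 10% | *f* = 15% |
|---|---|---|---|
| *R* = 60%, all failures (*q* = 1) | 63.2% | 66.7% | 70.6% |
| *R* = 60%, *q* = 0.8 | 62.1% | 64.4% | 67.1% |
| *R* = 60%, same failure rate as the rest (*q* = 0.4) | 60.0% | 60.0% | 60.0% |
| *R* = 50%, all failures | 52.6% | 55.6% | 58.8% |
| *R* = 70%, all failures | 73.7% | 77.8% | 82.4% |
| *R* = 60%, all retained | 60.0% | 60.0% | 60.0% |

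In counts, with an assumed 60 starters and 36 responders: 36/60 = 60.0% (exact 95% CI 46.5-72.4); dropping 3, 6 or 9 failures gives 36/57 = 63.2%, 36/54 = 66.7% (52.5-78.9) or 36/51 = 70.6%.

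The documents do not allow the direction or size of the time-point effect to be computed.

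**The case against.** A reader might infer that switched patients are also moved to the non-salvage response scale and leave the salvage endpoint. The documents do not support that. The rule in 7.7 moves only the window; it does not say the patient becomes a non-salvage patient or which outcome column applies. The SAP uses one scale for everyone, so a change of scale would not alter its table. Read literally, a patient who started and then stopped still had salvage treatment. SAP 4.4.4 lists therapies with start and end dates, so membership can be derived without the follow-up window. Addendum 2 assigns fluciclovine guidance from the agreed therapy text, not from quality of delivery. It follows that the inflation figures describe an exclusion nobody has written down.

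There are also safeguards: reasons are recorded on the CRF, and PSA levels are collected for all patients. For stopped therapy, treatment completion is not an obvious anchor, which may explain the exception. The endpoint is secondary, single-arm and descriptive.

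All of this stands, and it limits the point. It does not remove the timing gap in step 1, the conflict with 5.1 and 7.10, the lack of any criterion or deadline for the delivery judgement, or the silence on group membership. PSA collection for all does not help if it runs only to the end of the shorter window. That the judgement could follow sight of the PSA is inferred from that silence; the documents do not say that it would.

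**Conclusion.** The concern holds in this form: a written rule makes ascertainment of a named secondary endpoint depend on early stopping or on an undefined, untimed, open-label judgement, and the resulting window always closes at least 1 month before the endpoint PSA is due. Other protocol passages require that PSA without exception and must be reconciled with the rule. If data end with the switched window, the SAP scores these patients early or, with no PSA, not at all. Neither document says whether they count in the salvage denominator.

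The 3 to 11 point rise is an illustrative upper case. It rests on an assumed 60% rate, 5-15% of starters switched, every one a failure and every one dropped. If they are retained, denominator bias is zero, though the time-point inconsistency can remain. The plan should be changed, but the primary endpoint is not affected.

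**What to change.** - **Protocol:** reconcile 5.1, both parts of 7.7 and 7.10 so that collection of endpoint data does not depend on the delivery judgement. Where routine PSA results exist through the salvage window, use them. How treatment is managed is untouched.
- **SAP 5.4.2.1 and Addendum 2:** define the salvage group as all subjects who started radical salvage therapy. Keep them all in the denominator, on the SAP's existing single PSA scale.
- **Reporting:** give the number switched. The CRF reasons should identify them.
- **Sensitivity analysis:** count stopped, sub-optimally delivered or missing-PSA cases as non-response. Show those who completed as planned in a supportive table.

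The cost is wording, a little extra data entry and possibly a lower response rate. Protocol 11.3 reports that recruitment has ended, and Addendum 2 documents analyses after database lock. If further PSA entry is no longer possible, the SAP definition, the count and the sensitivity analysis should still be feasible from therapy dates and CRF reasons already recorded.

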7.8. Procedure for centres which perform choline PET as standard of care

In these participating centres, where the clinical team decides to investigate the subject with choline PET in addition to fluciclovine (^{18}F) PET/CT, this will be performed only after the fluciclovine (^{18}F) PET/CT report has been issued by the site, considered to formulate a revised management plan, and documented onto the appropriate CRF.

7.9. Discontinuation/Withdrawal of Participants from Study

Each participant has the right to withdraw from the study at any time. In addition, the Investigator may discontinue a participant from the study at any time if the Investigator considers it necessary for any reason including:

- Ineligibility (either arising during the study or retrospectively having been overlooked at screening)
- Significant protocol deviation
- Significant non-compliance with study requirements
- Withdrawal of consent
- Loss to follow up

Withdrawal from the study will not result in exclusion of the data for that participant from analysis provided all baseline study measures have been completed.

The reason for withdrawal will be recorded in the CRF. If the participant is withdrawn due to an AE/SAE, the Investigator will arrange for follow-up visits or telephone calls until the AE/SAE has resolved or stabilised.

7.10. Definition of End of Study

The fluciclovine (^{18}F) injection administration will be followed by a follow-up period which will continue for 6 months after instigation of management plan.

The end of the trial for an individual patient is defined as 6 months after instigation of their management plan. In patients who receive radical salvage therapy, the end of the trial is defined as the date of post-treatment PSA level.

The end of the study is defined as the date of database lock for data analysis, which is anticipated to occur within 12 weeks after the last patient has completed the 6 months post treatment follow up.

8. Risks and Benefits to Trial Participants

8.1. Benefits

The research scans may provide further clinical information regarding the patient's disease status that may not have been appreciated by other standard of care tests. If such information arises, this will be reported back to the responsible clinician to help direct the patient's further management. This may provide a direct benefit to the subject

8.2. Risks

The risks from the imaging studies to subjects mainly relate to the intravenous injection and the radiation emitted by the radiopharmaceutical. Intravenous injection carries a small risk of infection and haematoma.

Assuming an average annual background radiation exposure of 2.6mSv [ARSAC 2006], the radiation exposure from an individual administration of fluciclovine (¹⁸F) Injection would be equivalent to 3.2 years of background radiation, and the associated CT transmission scans would be equivalent to about 2.7 years of background radiation.

The above estimations are based on a mean effective dose per unit administered activity of 22.1µSv/MBq [55]. An administered activity of 370 MBq will result in an effective dose of 8.2mSv. A maximum effective dose of 7 mSv would be expected due to the CT transmission scan depending on the scanner (details of scanner-specific CT effective doses will be given in the Study Imaging Manual). The effective dose due to the helical CT acquisition will be in accordance with ALARA (As Low As Reasonably Achievable).

[figure not shown]
The total dose of 15.2mSv would be equivalent to 5.8 years of background radiation. This level of radiation exposure is in line with other common nuclear medicine procedures.

9. Intervention

[figure not shown]
9.1. Investigational Medicinal Product

The IMP is fluciclovine (¹⁸F) injection and consists of the radiolabelled compound fluciclovine (¹⁸F) together with excipients. Fluciclovine (¹⁸F) is a radiolabelled synthetic amino acid. The radioactive isotope ¹⁸F decays with a half-life of approximately 110 minutes.

Chemical formula

Chemical structure

Chemical name

(anti)-1-amino-3-[¹⁸F]fluorocyclobutane-1-carboxylic acid.

Physiological effects

Biodistribution and radiation dosimetry studies have demonstrated physiological uptake of fluciclovine (¹⁸F) to be highest in the liver and pancreas, with rapid biological clearance [56]. There is low albeit prolonged uptake in skeletal muscle and bone marrow, with clearance dominated by the tracer half-life [56]. A 370-MBq injection of fluciclovine (¹⁸F) results in an effective dose of 8.2 mSv.

Side effects

To date, fluciclovine (¹⁸F) has been found to be well-tolerated, with all treatment emergent AEs reported during clinical studies in humans to be mild in intensity, none requiring treatment [57]. AEs reported that were considered possibly related to receipt of fluciclovine (¹⁸F) include injection site reactions (redness, pain, bruising), dysgeusia and headache [57].

Safety considerations

All participants will be carefully observed and monitored throughout the study. A panel of blood tests comprising of serum biochemistry and haematology, and an electrocardiogram (ECG), will be performed during screening and at outpatient follow-up after the PET/CT scan.

On the day of scan, there will be a minimum number of two people in attendance. This will include a doctor or allied health care professional such as a nurse or radiographer, who is solely responsible for patient monitoring, safety and well-being. They will be aware of potential risks of fluciclovine (¹⁸F) injection, and appropriately trained in how to respond to any adverse sequelae arising. The second person in attendance will be a technician/ radiologist responsible for acquiring images. In the event of any untoward medical event occurring mid-scan, staff can reach the patient immediately. As in all clinical areas throughout the participating institutions, emergency drugs and equipment are readily available and staff are trained in their use. This includes supplementary oxygen and resuscitation equipment.

Visual monitoring of the injection site and monitoring of blood pressure and heart rate will be undertaken at intervals for up to 2 hours after injection prior to discharge. After the scan, the participants will be allowed to leave the PET/CT department but remain within the host site in between the monitoring intervals. Participants will receive a telephone consultation 24 -72 hours after completion of fluciclovine (¹⁸F) PET/CT to review any AEs that have occurred in the interim following discharge. Furthermore, participants will have further opportunity to report any AEs during their outpatient follow-up appointment 14 days later and at a telephone call 1 month post scan.

Participants will be recommended not to have close contact with pregnant women or young children for 6 hours after the injection, and to drink plenty of fluids for at least 5 days after the scan to aid urinary

clearance of the tracer. These guidelines are considered as the standard of care following injection of other ^{18}F labelled tracers.

IMP preparation

The sponsor will provide fluciclovine (^{18}F) injection as a sterile solution for injection. The fluciclovine (^{18}F) injection will be manufactured to Good Manufacturing Practice (GMP) at a qualified facility.

Before approval of the batch by the Qualified Person, the suitability of each preparation will be assessed by tests including radioactivity, HPLC, and pH quality control methods, against the drug product specification according to approved standard operating procedures (SOPs) of the GMP manufacturing site.

Supply and packaging

Sites will be provided with instructions for ordering the fluciclovine (^{18}F) injection for use in the study. The site must keep records of all shipments of IMP received, dispensing and disposal/destruction performed on site. The IMP will be delivered to the site by courier from the manufacturing facility as is appropriate to each facility. Information will be provided on each shielded container giving the batch number, radioactive concentration of injection (MBq/mL) at a stated time and date, and shelf life information. To ensure timely delivery, product may be dispatched from the manufacturing site before it has been approved for use by the Qualified Person. A written agreement will be required between the investigation site and the manufacturing site in which the investigation site undertakes not to administer the drug product until it has received written confirmation from the manufacturing site that the batch has been approved by the Qualified Person. Such confirmation will be provided, for example, by fax or e-mail.

The IMP is supplied as a solution for injection, 200 MBq/ml at the reference date and time in a vial from the GMP-validated manufacturing facility. Each vial is supplied in a container providing appropriate radiation shielding. The subject dose will be drawn just before administration. The radiochemical purity of fluciclovine (^{18}F) injection is not less than 95% during the shelf life of the product.

Stability and storage

The in-use shelf life of fluciclovine (^{18}F) injection is 10 hours from the end of synthesis and must not be used beyond this limit. The expiry date and time is included on the product label. Fluciclovine (^{18}F) injection must be kept in a locked, restricted access area when not in use. Fluciclovine (^{18}F) injection should be stored at room temperature in a shielded container and in accordance with national regulations for radioactive materials. The precautions normally taken when handling radioactive materials should be observed. All non-radioactive IMP shielded containers must be returned to the sponsor/manufacturing site. Vials that are radioactive, or contained radioactive products must be destroyed at the PET centre after the study and after overall drug accountability have been completed by the sponsor or its representative. A list of IMP doses and other materials that were returned, or destroyed, must be prepared and signed by the principal investigator. An overall accountability form of the IMP will be prepared and supplied by the sponsor and completed properly. An explanation for any discrepancy must be provided.

Waste must be disposed of according to national regulations for radioactive material. The shielded container and transport case that the product is delivered in are the property of the manufacturing site. After use of the product, they must be stored securely and made available for collection on the reasonable notice of BED or the manufacturer.

IMP administration

Each individual drawn subject dose will only be administered to the subject assigned to it. No patient is to receive more than 5ml of the undiluted product.

Since the drug product vial could contain more radioactivity than is required for a 1-subject dose at the time of administration, the correct volume needs to be calculated before administration. The volume to be withdrawn and injected must be calculated from the required dose, the radioactive concentration and the reference date and time, and documented (must not exceed 5ml). After the dose has been given, subsequent doses may be withdrawn for additional subjects. When the study site receives the dose in a vial and prior to administration, the activity in the vial containing the IMP will be measured in a dose calibrator. The required dose will then be drawn into a syringe, with the activity confirmed using the same dose calibrator. Post injection, remaining activity within the syringe would be measured and the difference of pre- and post-injection syringe activities, accounting for physical decay, would be used to calculate the actual activity administered into the cannula. Appropriate dose calibrator scale factors for ^{18}F (as per manufacturer's specifications) should be applied to ensure accuracy of all activity measurements and be documented. Aseptic conditions must be observed during withdrawal of a dose from the vial, including microbial decontamination of the rubber stopper with a suitable disinfectant before removal of a dose.

Prior to PET/CT, $370 \pm 20\%$ MBq of fluciclovine (^{18}F) (not more than 5ml of product) diluted up to 10 ml with saline (sodium chloride IV infusion 0.9% w/v) will be administered. The administration will be by intravenous push (5-10 seconds) followed by a 10 ml saline flush. Fluciclovine (^{18}F) will be injected through a cannula (or indwelling catheter) with the subject lying in a supine position and in an antecubital vein or another vein that will provide access. The administration site will be evaluated pre- and post administration for any reaction (e.g. bleeding, haematoma, redness, or infection). Documentation of the IMP administered to a subject will be recorded according to standard of care and on the appropriate CRF, including date, vial number, total volume, total radioactivity, start/stop time of administration, and injection site.

Compliance with trial treatment

Participants will receive the fluciclovine (^{18}F) injection under direct supervision of study personnel. Each administration volume and total radioactivity injected will be checked. The label on the IMP container will include the batch number, expiry date/time activity in MBq, reference date/time, and volume. The batch number and volume per administration will be recorded in each subject's CRF/source document.

Concomitant medication

In general, concomitant medications and therapies deemed necessary for the supportive care and safety of the subject are allowed, provided their use is documented in the participant's records and on the appropriate CRF. Participants should be maintained on the same medications throughout the study period, if medically feasible.

